### 7.2 PARTICIPANT DISCONTINUATION/WITHDRAWAL FROM THE STUDY

Participants are free to withdraw from participation in the study at any time upon request.

An investigator may discontinue a participant from the study for the following reasons:

- Significant study intervention non-compliance, unless varying compliance is an aspect of the study objectives
- Lost-to-follow up; unable to contact subject (see **Section 7.3, Lost to Follow-Up**)
- Any event or medical condition or situation occurs such that continued collection of follow-up study data would not be in the best interest of the participant or might require an additional treatment that would confound the interpretation of the study
- The participant meets an exclusion criterion (either newly developed or not previously recognized) that precludes further study participation

The reason for participant discontinuation or withdrawal from the study will be recorded. Subjects who sign the informed consent form and are randomized but do not receive the study intervention may be replaced. Subjects who sign the informed consent form, and are randomized and receive the study intervention, and subsequently withdraw, or are discontinued from the study, will not be replaced.

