#### 5.2 EXCLUSION CRITERIA

An individual who meets any of the following criteria will be excluded from participation in this study:

1. Any psychiatric diagnoses other than an SUD
2. Medical disorder(s) that may affect the central nervous system; medications that affect the central and autonomic nervous system; or a positive pregnancy test result (females)
3. Excluding cannabis, evidence of recent (past month) illicit drug use.

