### 6.3 MEASURES TO MINIMIZE BIAS: RANDOMIZATION AND BLINDING

*To minimize potential biases, participants are randomized based on automatic covariate conducted by Co-I using an adaptive algorithm. Participants are blinded to the intervention. Specifically, they were told that they will be engaged in body-mind intervention, without knowing whether or not the intervention they received is the experimental manipulation or control intervention. See methods of analysis in **Section 9, Statistical Considerations** for details on randomization. Additionally, research staff who assesses participants are also blinded of the participants' intervention condition. Randomization code is maintained by the Co-I. A planned breaking of randomization code and blinding would occur for any participants who reported serious adverse events. The PI and Co-I will identify which group the participant is in, without the need for research staff to be involved in knowing the participant's intervention group.*

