## 7 STUDY INTERVENTION/EXPERIMENTAL MANIPULATION DISCONTINUATION AND PARTICIPANT DISCONTINUATION/WITHDRAWAL

### 7.1 DISCONTINUATION OF STUDY INTERVENTION/EXPERIMENTAL MANIPULATION

If a clinically significant finding is identified (including, but not limited to changes from baseline) after enrollment, the investigator or qualified designee will determine if any change in participant management is needed. Any new clinically relevant finding will be reported as an adverse event (AE).

The data to be collected at the time of study intervention discontinuation will include the following:

- The reason(s) for discontinuing the participant from the intervention, and methods for determining the need to discontinue
- If the participant is due to complete assessments within 1 weeks of being discontinued from the study intervention, those assessments will be administered at the time of discontinuation; if the next scheduled assessments are more than 1 week from the discontinuation date, the next scheduled assessment will not be administered. Thereafter, the participant will be not included in all future scheduled assessments, as they did not participate in the intervention.

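### Sections 7.1 and 7.2 allow outcome collection to stop for randomised participants because of events after randomisation, which biases the arm comparison if such removal differs by arm

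*Combined protocol and SAP*

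**What the plan says.** Section 7.2 opens its list with "An investigator may discontinue a participant from the study for the following reasons". Two of the reasons matter here. One is "The participant meets an exclusion criterion (either newly developed or not previously recognized) that precludes further study participation". The other is an event or condition after which further follow-up would be against the participant's interest, or which "might require an additional treatment that would confound the interpretation of the study". The reason for discontinuation is recorded, and a participant who has received the intervention is not replaced.

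The exclusion criteria in Section 5.2 include "Excluding cannabis, evidence of recent (past month) illicit drug use", "Any psychiatric diagnoses other than an SUD" and "medications that affect the central and autonomic nervous system".

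Section 7.1 covers stopping the intervention, as distinct from leaving the study. If the next assessment falls within one week, it is done at the time of stopping; if it is further off, it is not done. The section ends: "Thereafter, the participant will be not included in all future scheduled assessments, as they did not participate in the intervention".

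Section 9.3 restricts the analysis to participants who attended all ten sessions and have primary endpoint data. Section 9.4.2 deletes cases with missing data. Section 9.2 mentions attrition only in connection with power. On access to allocation, Section 6.3 says "Randomization code is maintained by the Co-I".

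**The concern.** Entry criteria define who is randomised. Applied again after randomisation, they make staying in the endpoint depend on what happens to the participant. In polysubstance users, use of a further illicit drug, a new psychiatric diagnosis, or a new medication acting on the nervous system can each follow from the course of the condition or from seeking help for it.

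The study rationale in Section 2.1 expects the intervention to act on self-control regions of the brain and so to reduce substance use. On the trial's own hypothesis, then, arm can influence substance use, and substance use can influence these grounds for removal. Losses that differ by arm are a plausible consequence of the intervention working.

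What is at stake is the comparability of the arms at Day 31. A scan that was never taken cannot be recovered by redefining the analysis set. No planned analysis uses the recorded reasons, and the plan contains no sensitivity analysis for missing outcomes.

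**Working it through.** **Inputs from the documents.** Ten intervention visits between Day 3 and Day 30, and the post-intervention scan on Day 31 ±2 (Section 1.3). The one-week rule (7.1). 70 enrolled, 35 per arm, 20% loss, 56 completers (5.5, 9.2). Expected between-arm effect 0.80 SD with 90% power (9.2).

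**Inputs assumed.** Two-sided alpha of 0.05 (9.2 states none), equal spacing of sessions, and all removal rates and outcome gaps in steps 4 and 5.

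**1. The plan's own figure.** With 35 per arm and d = 0.80, power is 91.0% (two-sample t) or 91.7% (normal approximation), so the stated 90% is reproduced. With 20% loss, 35 × 0.80 = 28 per arm and power is 83.6% or 84.9%. These figures concern precision only. They say nothing about who is lost.

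**2. Which developments give a ground for removal.**

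| Development after randomisation | Ground under 7.2? |
|---|---|
| Illicit drug use other than cannabis | Yes, through 5.2 |
| Psychiatric diagnosis other than an SUD | Yes, through 5.2 |
| Medication acting on the central and autonomic nervous system | Yes, through 5.2 |
| Event that might need confounding treatment | Yes, directly |
| Heavier alcohol, tobacco or cannabis use, or an SUD to these | Not by itself; 5.1 allows these SUDs |
| Criterion already met at entry but missed | Yes, but this is baseline ineligibility, not disease course |

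**3. Timing under 7.1.** 31 − 7 = Day 24. Someone who stops before about Day 24 gets no post-intervention scan (Day 22 to 26 if the visit moves within its window: 29 − 7 and 33 − 7). Ten equally spaced sessions fall on Days 3, 6, …, 30, and seven of them fall on or before Day 21. That participant may therefore have attended 7 of 10 sessions and is still described as not having taken part. Someone who stops later but short of ten sessions can be scanned, but 9.3 leaves that scan out of the analysis.

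**4. Bias if removal differs by arm.** Let p be the proportion removed in an arm and g the mean change in the removed minus that in the retained. The full-arm mean is (1 − p) × retained + p × removed, so the retained mean is the full mean − p × g. With the same g in both arms, the bias in the arm difference has size (difference in p) × g:

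- 0.10 × 0.5 SD = 0.05 SD, and 0.05 / 0.80 = 6% of the planned effect
- 0.20 × 1.0 SD = 0.20 SD, and 0.20 / 0.80 = 25% of the planned effect
- equal p and equal g: 0

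**5. Cross-check with another model.** Suppose those with the worst course are removed, and the score driving removal correlates at r with endpoint change. Removing a fraction f shifts the retained mean by r × φ(z) / (1 − f), where z is the f-quantile of the standard normal and φ its density. With r from 0.2 to 0.5 and 35 randomised per arm:

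| Removed, arm vs arm | Bias (SD) | Type I error |
|---|---|---|
| 20% vs 20% | 0 | 5.0% |
| 15% vs 25% | 0.03 to 0.08 | 5.1% to 5.9% |
| 10% vs 30% | 0.06 to 0.15 | 5.6% to 8.7% |

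The sign depends on which arm loses more. The two models agree on the order of size. Neither is an estimate for this trial.

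**The case against.** Several points on the other side are sound and limit the claim.

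- **Worsening use as such.** A reader might infer that anyone whose substance use worsens is removed. The documents do not support that: more drinking, smoking or cannabis use meets no exclusion criterion. The rule is also permissive, and it applies only where the criterion precludes further participation, although the plan does not say which criteria do.
- **Follow-up to Day 90.** A reader might count events up to Day 90. The primary endpoint compares baseline with Day 31, so only about the first three to four weeks matter for it. Eligibility review is scheduled only at pre-screening, so detection would rest largely on adverse event enquiry and self-report.
- **One rule or two.** The one-week cut-off belongs to 7.1. Section 7.2 does not say that it applies to people discontinued from the study.
- **Removal in knowledge of the arm.** A reader might infer this because the Co-I holds the code. Nothing says that the Co-I makes decisions under 7.2, and assessors are blinded. What stands is that the plan does not rule it out.
- **Size.** The 14 of 70 expected to be lost (20% × 70) covers all causes. Section 5.5 names illness and relocation and allots nothing to this clause.
- **Purpose.** In a mechanistic imaging study, wishing to limit confounding by new medication is defensible. That aim can be met by flagging such scans and does not require leaving them untaken.

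The strongest objection is that extra scans alone would change little, because 9.3 drops anyone with fewer than ten sessions whether scanned or not. That is right, and 9.3 must be changed together with 7.1 and 7.2.

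**Conclusion.** The point holds in a limited form. Sections 7.1 and 7.2 allow outcome collection to end for randomised participants because of events after randomisation, some of them related to the course of substance use or to seeking treatment. Sections 9.3 and 9.4.2 then exclude these participants. The reason 7.1 gives for stopping assessments is untrue of anyone who attended sessions.

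If such removal differs by arm, the primary comparison is biased. How often it will occur, its direction and its size cannot be derived from the documents. The range of 0.05 to 0.20 SD, or 6% to 25% of the planned effect, rests wholly on assumed removal differences and outcome gaps; it should not be read as an expected bias. If removal acts equally in both arms, the bias is zero. The case for change rests on the mechanism and on how little it costs to close.

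**What to change.** 1. **Section 7.1.** Strike the one-week cut-off and the closing clause that treats the person as a non-participant. Offer every randomised participant who remains willing the scheduled Day 31 and Day 90 scans, whether or not sessions stop.
2. **Section 7.2.** State that newly developed 5.2 criteria and new treatments do not by themselves end study assessments. Keep exceptions for withdrawn consent, unsafe scanning and the participant's best interest. Record the event and its date.
3. **Section 9.3.** Make the primary analysis all randomised participants with available endpoint data, and keep the ten-session completers as a supporting analysis. Without this the retained scans would mostly go unused.
4. **Section 6.3 or 7.2.** Have decisions to end assessments made without access to the randomisation code.

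Decisions about the intervention itself stay with the clinician and are not touched.

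The cost is protocol wording and a small number of additional scans within the 70 participants already planned. The ceiling is 14 participants, or 14 × 2 = 28 scans over Days 31 and 90. The real number would be lower, since people who relocate, withdraw or cannot be reached will not be scanned. Some retained scans will come from people on other treatments; these can be flagged and examined in a sensitivity analysis.

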### 7.3 LOST TO FOLLOW-UP

A participant will be considered lost to follow-up if he or she fails to return for 1 scheduled visit and study staff are unable to contact the participant after at least 3 attempts.

The following actions must be taken if a participant fails to return for a required study visit:

- The site will attempt to contact the participant, reschedule the missed visit within 1 week, counsel the participant on the importance of maintaining the assigned visit schedule and ascertain if the participant wishes to and/or should continue in the study
- Before a participant is deemed lost to follow-up, the investigator or designee will make every effort to regain contact with the participant (where possible, 3 telephone calls and, if necessary, a certified letter to the participant's last known mailing address or local equivalent methods).
- Should the participant continue to be unreachable, he or she will be considered to have withdrawn from the study with a primary reason of lost to follow-up.

## 8 STUDY ASSESSMENTS AND PROCEDURES

### 8.1 ENDPOINT AND OTHER NON-SAFETY ASSESSMENTS

*The study involves assessing participants at baseline, post-intervention, and one-month follow-up. The participant will be screened for eligibility after consenting. They will fill out demographic questionnaires and MRI screening form to determine their eligibility. Next, they will undergo behavioral and brain assessments by trained research staff and/or MRI technician. All non-brain assessments will be conducted at PI's lab for all participants to decrease variability. All brain assessments will be conducted at Barrow Neurological Institute for all participants to decrease variability.*

*Below is a list and description of the assessments:*

- **Imaging assessments**  
*MRI Scan – provides images of brain structure and function*
- **Administration of questionnaires, interviews**  
*Behavioral assessments – demographic questionnaire, subjective reports of polysubstance use*

### 8.2 SAFETY ASSESSMENTS

*N/A*

### 8.3 ADVERSE EVENTS AND SERIOUS ADVERSE EVENTS

#### 8.3.1 DEFINITION OF ADVERSE EVENTS

This protocol uses the definition of adverse event from 21 CFR 312.32 (a): any untoward medical occurrence associated with the use of an intervention in humans, ***whether or not considered intervention-related.***

### 8.3.2 DEFINITION OF SERIOUS ADVERSE EVENTS

*This protocol uses the definition of serious adverse event includes: (a) Death; (b) Hospitalization (initial or prolonged); (c) Life-threatening condition; (d) Disability or Permanent Damage; (e) Other Serious (Important Medical Events).*

### 8.3.3 CLASSIFICATION OF AN ADVERSE EVENT

#### 8.3.3.1 SEVERITY OF EVENT

For adverse events (AEs) not included in the protocol defined grading system, the following guidelines will be used to describe severity.

- **Mild** – Events require minimal or no treatment and do not interfere with the participant's daily activities.
- **Moderate** – Events result in a low level of inconvenience or concern with the therapeutic measures. Moderate events may cause some interference with functioning.
- **Severe** – Events interrupt a participant's usual daily activity and may require systemic drug therapy or other treatment. Severe events are usually potentially life-threatening or incapacitating. Of note, the term "severe" does not necessarily equate to "serious".

#### 8.3.3.2 RELATIONSHIP TO STUDY INTERVENTION/EXPERIMENTAL MANIPULATION

All adverse events (AEs) will have their relationship to study procedures, including the intervention, assessed by an appropriately-trained clinician based on temporal relationship and his/her clinical judgment. The degree of certainty about causality will be graded using the categories below.

- **Related** – The AE is known to occur with the study procedures, there is a reasonable possibility that the study procedures caused the AE, or there is a temporal relationship between the study procedures and the event. Reasonable possibility means that there is evidence to suggest a causal relationship between the study procedures and the AE.
- **Not Related** – There is not a reasonable possibility that the study procedures caused the event, there is no temporal relationship between the study procedures and event onset, or an alternate etiology has been established.

#### 8.3.3.3 EXPECTEDNESS

A clinician with appropriate expertise in medical care will be responsible for determining whether an adverse event (AE) is expected or unexpected. An AE will be considered unexpected if the nature, severity, or frequency of the event is not consistent with the risk information previously described for the study procedures.

#### 8.3.4 TIME PERIOD AND FREQUENCY FOR EVENT ASSESSMENT AND FOLLOW-UP

The occurrence of an adverse event (AE) or serious adverse event (SAE) may come to the attention of study personnel during study visits and interviews of a study participant presenting for medical care, or upon review by a study monitor.

All AEs, not otherwise precluded per the protocol, will be captured on the appropriate case report form (CRF). Information to be collected includes event description, time of onset, clinician's assessment of severity, relationship to study procedures (assessed only by those with the training and authority to make a diagnosis), and time of resolution/stabilization of the event. All AEs occurring while on study will be documented appropriately regardless of relationship. All AEs will be followed to adequate resolution.

Any medical or psychiatric condition that is present at the time that the participant is screened will be considered as baseline and not reported as an AE. However, if the study participant's condition deteriorates at any time during the study, it will be recorded as an AE.

Changes in the severity of an AE will be documented to allow an assessment of the duration of the event at each level of severity to be performed. Documentation of onset and duration of each episode will be maintained for AEs characterized as intermittent.

PI will record events with start dates occurring any time after informed consent is obtained until 7 (for non-serious AEs) or 30 days (for SAEs) after the last day of study participation. At each study visit, the investigator will inquire about the occurrence of AE/SAEs since the last visit. Events will be followed for outcome information until resolution or stabilization.

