### 1.2 SCHEMA

**Figure 1. Flowchart of screening, inclusion, and assessment process**

### 1.3 SCHEDULE OF ACTIVITIES

	Pre-screening	Visit 1 Day 1	Visit 2 to Visit 11 Day 3 ±1 to Day 30±1	Visit 12 Day 31 ±2	Visit 13 Day 90 ±2
Review Eligibility	X				
Informed Consent		X			
Demographics		X			
Outcome Evaluation					
Brain Assessment (MRI scan)		X		X	X
Cognitive Assessment (Self-control tasks)		X		X	X
Randomization		X			
Control & Experimental Interventions		X	X		
Adverse Events Reporting		X	X	X	X

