#### 4.4 END-OF-STUDY DEFINITION

A participant is considered to have completed the study if he or she has completed the baseline assessment, 10 intervention sessions, and post-intervention assessment.

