#### 10.1.6 SAFETY OVERSIGHT

Safety oversight will be under the direction of a Data and Safety Monitoring Board (DSMB) composed of individuals with the appropriate expertise, including clinical trials and intervention. Members of the DSMB will be independent from the study conduct and free of conflict of interest. The DSMB will meet at least semiannually to assess safety and efficacy data from each arm of the study. The DSMB will operate under the rules of an approved charter that will be written and reviewed at the organizational meeting of the DSMB. At this time, each data element that the DSMB needs to assess will be clearly defined. The DSMB will provide its input to NCCIH via annual report.

---

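### The adverse event recording window ends with an undefined last day of participation, so participants who stop training are observed for much less time and by-arm harm tallies can be distorted if stopping differs by arm

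*Combined protocol and SAP*

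**What the plan says.** - **Recording period (Section 8.3.4).** Events are recorded if they start after consent and "until 7 (for non-serious AEs) or 30 days (for SAEs) after the last day of study participation". The closing day is not defined there or elsewhere.
- **How events are found (Section 8.3.4).** "At each study visit, the investigator will inquire about the occurrence of AE/SAEs since the last visit". Events may also come to notice when a participant seeks medical care or when a study monitor reviews records. Recorded events are followed until they resolve or stabilise.
- **After stopping training (Section 7.1).** An assessment due within one week is done at the time of stopping, and a later one is not done. "Thereafter, the participant will be not included in all future scheduled assessments, as they did not participate in the intervention".
- **Visits (Section 1.3).** The row "Adverse Events Reporting" is marked at every visit from Day 1 up to "Visit 13 Day 90 ±2".
- **Completion (Section 4.4).** A participant counts as having completed the study when he or she "has completed the baseline assessment, 10 intervention sessions, and post-intervention assessment". That point is about Day 31, and the Day 90 visit is not part of it. The synopsis gives a participant duration of three months, and Section 8.1 places the follow-up at one month.
- **Use of the data.** Section 9.4.4 (safety analyses) is marked not applicable. Under Section 10.1.6 the DSMB meets at least twice a year to "assess safety and efficacy data from each arm of the study".

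**The concern.** The window closes relative to each person's own participation, not at a day common to all. Read with Section 7.1, stopping training also ends the scheduled contacts at which staff ask about events. Section 1.3 shows no contact after the last visit attended, so a stopper's 7- or 30-day tail depends on the passive routes in Section 8.3.4.

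Two things are at stake. First, new events that begin after a stopper's window closes are not collected in either arm, and no later analysis can recover them. Stopping can itself follow a medical event or a newly met exclusion criterion (Section 7.2), so observation may end because something has gone wrong. Second, if one arm loses more participants, or loses them earlier, its crude event count will be lower at the same true rate. With 35 per arm, a few missed events could change a by-arm tally.

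The closing day is unclear for completers too. Sections 1.3 and 4.4 give different end points for the same person.

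**Working it through.** **Inputs from the protocol.** Recording tail w = 7 days (non-serious) or 30 days (serious), Section 8.3.4. Last visit L = Day 90 (Section 1.3), or Day 31 if participation ends at completion (Sections 1.3 and 4.4). Enrolment 70, planned dropout 20% overall (Section 5.5); 35 per arm (Section 9.2).

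**Assumptions.** A stopper's participation ends on the day of stopping, s. The protocol gives no stop day; I use Day 10, with a range of Day 3 to Day 30, which spans the training visits in Section 1.3. It gives no dropout by arm, so the arm splits below are illustrations.

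**The plan's own figure.** 70 × (1 − 0.20) = 56 completers, as Section 5.5 states, leaving 70 − 56 = 14 who do not complete.

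**Length of the window.** Coverage ends on day L + w for a completer and s + w for a stopper.

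- Completer, last day 90: 90 + 7 = 97 and 90 + 30 = 120.
- Completer, last day 31: 31 + 7 = 38 and 31 + 30 = 61.
- Stopper at Day 10: 10 + 7 = 17 and 10 + 30 = 40. The Day 31 assessment is 21 days away, so the one-week exception in Section 7.1 does not apply.

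Stopper's share = (s + w)/(L + w):

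| Stop day | Non-serious: end day | of 97 | of 38 | Serious: end day | of 120 | of 61 |
|---|---|---|---|---|---|---|
| 3 | 10 | 10% | 26% | 33 | 28% | 54% |
| 10 | 17 | 18% | 45% | 40 | 33% | 66% |
| 15 | 22 | 23% | 58% | 45 | 38% | 74% |
| 30 | 37 | 38% | 97% | 60 | 50% | 98% |

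**Mean observation by arm.** With share d stopping on day s, mean = d(s + w) + (1 − d)(L + w). At an equal, constant event rate, the ratio of means is the ratio of expected crude counts.

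Non-serious events, s = 10, L = 90:

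- 20% in each arm: 0.2 × 17 + 0.8 × 97 = 81.0 in both; ratio 1.00.
- 25% against 15%: 0.25 × 17 + 0.75 × 97 = 77.0; 0.15 × 17 + 0.85 × 97 = 85.0; ratio 0.91.
- 30% against 10%: 0.3 × 17 + 0.7 × 97 = 73.0; 0.1 × 17 + 0.9 × 97 = 89.0; ratio 0.82.

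For 30% against 10%, moving the stop day from 3 to 30 gives ratios of 0.80 to 0.87 (non-serious) and 0.84 to 0.90 (serious).

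The same 30% against 10% split at Day 10 with L = 31:

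- Non-serious: 0.3 × 17 + 0.7 × 38 = 31.7; 0.1 × 17 + 0.9 × 38 = 35.9; ratio 0.88.
- Serious: 0.3 × 40 + 0.7 × 61 = 54.7; 0.1 × 40 + 0.9 × 61 = 58.9; ratio 0.93.

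**With a common end.** If everyone is followed to the same day, the ratio is 1.00 whatever the pattern of stopping.

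**The case against.** The strongest reply is that none of this shows a biased comparison. The protocol gives one overall dropout rate and nothing by arm, and equal stopping leaves mean observation equal. No statistical comparison of harm is planned. The DSMB's data elements will be set at its organisational meeting under its charter, and these may include observation time. All of this stands, and it makes the arm-level concern conditional.

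The size also depends on an ambiguous anchor. If a completer's participation ends at Day 31, a completer whose last session is Day 30 is covered for 38 − 30 = 8 days afterwards, against 7 for a stopper whose last day is a session day. The gap after the last session nearly vanishes, although the gap in total time remains. This also stands, which is why both readings are shown.

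A reader might infer that events are sought only at visits, or that stoppers are the people most likely to have been harmed. The documents support neither. Section 8.3.4 names other routes, and Section 5.5 attributes dropout in earlier longitudinal studies to illness or relocation. An event that prompts stopping begins before it, so it falls inside the window and is followed up. What can be lost is a new event with later onset.

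Finally, a window tied to participation is a common design choice, and the protocol foresees little intervention risk beyond boredom (Section 2.3.1). That limits the urgency but does not resolve the conflict between sections.

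**Conclusion.** The point holds as a gap in data collection with a conditional effect on by-arm tallies. Provided that participation ends on the day of stopping, a Day 10 stopper is covered for 17 of 97 days (non-serious) and 40 of 120 (serious) relative to someone followed to Day 90, or 17 of 38 and 40 of 61 on the Day 31 reading. Late new events in stoppers are under-recorded in both arms, however stopping is distributed. Separately, and with no assumption about dropout, the same completer's window for non-serious events is 38 or 97 days depending on which section is followed.

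The tempting stronger conclusion, that arm comparisons of harm are biased, is not supported. It needs stopping to differ by arm in amount or timing, which the documents neither state nor assume, and the only by-arm look they describe is the DSMB's. The 0.82 ratio illustrates what an assumed 30% against 10% split would do. It is not a forecast.

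The amendment is worth making because it is cheap and uncollected events cannot be recovered.

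**What to change.** 1. Reconcile Sections 1.3, 4.4, 7.1, 8.1 and 8.3.4. State one end to adverse event and serious adverse event recording that is the same for every randomised participant who has not withdrawn consent, whether or not training is stopped.
2. For stoppers who can be reached, ask the same adverse event questions by phone at the times of the existing Day 31 and Day 90 visits.
3. Show person-time at risk by arm beside the event counts in the DSMB safety tables.

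Anchoring the window to each person's last session would not be enough. For non-serious events, a Day 10 stopper would still have 17 days, against 30 + 7 = 37 for someone whose last session is Day 30.

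**Cost.** A wording amendment, a little table programming, and at most two short calls for each reachable stopper. At the planned dropout that is at most about 14 of 70 participants, or 2 × 14 = 28 calls, using contact details the study already collects (Section 5.5). Some of the 14 will have withdrawn consent or be lost to follow-up, so the calls will be fewer and some events will still be missed.
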